8.2. Screening and Enrollment in the Run-in Period (Visit 1)

Subjects who have a confirmed history of micro- or macroalbuminuria (at least two out of three consecutive urinary AER or ACR in micro- or macroalbuminuria range as defined in Section 5.1) will not need to bring a sample of urine to Visit 1. Subjects who have incomplete or no previous evidence of micro- or macroalbuminuria or have unknown albuminuria status, will be mailed two containers before Visit 1 along with instructions for collecting two samples of urine from their first morning void and bringing it to the visit to confirm the presence of micro- or macro-albuminuria. During **Visit 1**, subjects will undergo the following procedures:

- Obtain written informed consent.
- Collect prior and concomitant medications, and demographic information.
- Measure weight and height.
- Measure vital signs.
- Perform pregnancy test in women of childbearing potential.
- Review the fetal risks of RAS blockade.
- Collect samples for clinical laboratory assessment.
- Provide a container and instructions for an overnight urine collection to be made immediately before Visit 3 if subject qualifies for the study.
- Upon receipt of laboratory measurements, confirm that inclusion/exclusion criteria are met.

The Screening Visit can be repeated after 4 weeks if the circumstances that led to the exclusion of a participant are deemed to have possibly changed.

Patients on losartan with uric acid levels between 4.2-4.4mg/dl at initial screening may, with the agreement of the patient and their PCP, be switched to another angiotensin receptor blocker (ARB) and have their uric acid level rechecked in one month.

8.3. Run-in Period (Visits 2, 3, and 4)

Starting at **Visit 2**, eligible subjects who agree to participate in the study will enter a run-in period of 9 weeks (see note at the end of this section for exceptions to this duration). During this visit, subjects will undergo the following procedures:

- Obtain written informed consent to enter run-in period (if the consent at V1 was only for screening).
- Review the fetal risks of RAS blockade.
- Collect medical history.
- Perform ECG.
- Collect concomitant medications.
- Measure weight and height.
- Measure vital signs.
- Physical Examination
- Obtain a urine pregnancy test

RAS antagonist treatment will be standardized, and BP, if elevated (>140/90 mm Hg), normalized. Letters will be written to the participants' physicians informing them about the study and notifying them of the study's protocol RAS blocker requirements and blood pressure goals. The letter will propose active participation of the participants' physicians in blood pressure management with the

availability of advice from the PERL site physicians and, if needed, the PERL Drug monitoring Committee for out of range blood pressure values during the course of the study. The run-in period will start at **Visit 2**. If a participant is already on a RAS Blocker, its dose will be increased, if necessary, to make it at least equivalent to ramipril 10 mg (if on ACE inhibitor [ACEI]) or irbesartan 300 mg (if on an angiotensin receptor blocker [ARB]), if acceptable to the patient's primary physician, if tolerated and if not contraindicated (see below). Participants who were not taking a RAS Blocker will be prescribed and instructed to start taking 10 mg of ramipril daily or 300 mg of irbesartan daily (if ramipril is contraindicated or has side effects) or another ACE inhibitor or ARB at equivalent doses if there are impediments to the use of ramipril or irbesartan. Participants who have contraindications to RAS blockers (e.g., SBP<100 mmHg, K⁺>5.5 mEq) or do not have evidence or history of micro- or macroalbuminuria (as defined in 5.1.4), are normotensive, and are not being treated with RASB or other anti-hypertensive agents will not be treated with these drugs, as this represents the standard of care.

Participants who are placed for the first time on RAS blockers as part of this study will start with half a dose; if there are no side effects, this will be increased to a full dose at Visit 3 and their serum K⁺ and creatinine measured at a local laboratory after 2 weeks. RAS blockers will be immediately discontinued in the case of allergic reactions or angioedema or the suspicion of pregnancy. If pregnancy is confirmed, the patient will remain off RAS blockade until the pregnancy and breast-feeding are completed. Their dose will be decreased to half if symptomatic hypotension (SBP<100%) or intractable cough develops, followed by their discontinuation. For persistent cough with ramipril or other ACEI, irbesartan or another ARB will be prescribed in substitution of the ACEI.

In the case of hyperkalemia (K⁺ >6.0 mEq) or serum creatinine elevation (>30% increase over baseline values), the participant will be asked to immediately obtain a confirmatory lab value at their local lab or clinical site and then discontinue the RAS blocker while awaiting this confirmatory result. If confirmed, the participant will resume RAS blockade at half dose 72 hours later and will have repeat labs one week later. If the problem persists, RAS blockade will be discontinued for the remainder of the trial and BP managed by alternate drugs (see below). If not confirmed, the participant will resume RAS blockade at their usual dose and have a repeat lab check one week later. These same steps will be taken if hyperkalemia develops during the trial.

Participants will continue to take any other antihypertensive drug that they may have been taking before study entry. Participants will be provided with a blood pressure monitoring device (if they do not already have access to one), will be trained on its use, and will be instructed to periodically monitor their blood pressure at home and to record the results into a BP diary, and to communicate them to study personnel if values are abnormal.

If hypotension develops (SBP<100 or significant lightheadedness), the dosage of non-RAS antagonist antihypertensive drugs will be progressively reduced until discontinuation, followed by a reduction of RAS blockers to half the dose and their discontinuation if the problem persists. If BP is found to be elevated (>140/90 mm Hg) on three consecutive occasions, the dosage of existing non-RAS antagonists antihypertensive drugs will be maximized, followed, if necessary, by the introduction of antihypertensive drugs of a different class. These will be chosen in collaboration with the other health care providers that are involved in managing the participant's anti-hypertensive therapy³³. If the goal of BP ≤140/90 is not achieved with these drugs, a Drug Monitoring Committee conference call will be convened to consider the possibility of causes of hypertension other than diabetic nephropathy and discuss alternative therapeutic approaches. BP will continue to be monitored and the anti-hypertensive therapy to be adjusted in a similar way throughout the study.

After 2 weeks of run-in, participants will come in for **Visit 3** during which they will undergo the following procedures:

- Obtain interval medical history (with special emphasis on CVD events).
- Review concomitant medications and AEs

- Review RASB and BP therapy.
- Collect samples for clinical laboratory assessments as outlined in Figure 1.
- Perform pregnancy test in women of childbearing potential.
- Be provided with a container and instructions for an overnight urine collection to be made immediately before Visit 4.

After 6 weeks of run-in, participants will come in for **Visit 4** during which they will undergo the following procedures:

- Obtain interval medical history (with special emphasis on CVD events).
- Conduct a physical exam (if deemed to be required by the study physician)
- Review concomitant medications and AEs
- Review BP therapy.
- Review the fetal risks of RAS blockade.
- Measure height, weight and vital signs.
- Perform ECG.
- Collect samples for clinical laboratory assessments (including HLA B*58:01) as outlined in Figure 1.
- Perform pregnancy test in women of childbearing potential.
- Measure iohexol GFR.

If normal blood pressure control is not achieved at Visit 4, the run-in period may be extended for two more weeks after which participants will be examined as in Visit 4 (Visit 4A). In this event, the GFR measurement scheduled for Visit 4 will be conducted at Visit 4A. Participants whose SBP is >150 or whose DBP is >95 mmHg at the end of the run-in period will be discontinued from the study (prior to randomization).

IMPORTANT: Visit 2 and Visit 3 can be skipped, i.e., a participant can move directly from Visit 1 to Visit 4, if the following criteria are met at Visit 1:

1. The participant is eligible based on the results of Visit 1 assessments, including laboratory values;
 2. Blood pressure is <140/90 mmHg;
- AND
3. The participant meets one of the following criteria:
 - Has been treated with a RASB for at least two months at a dose at least equivalent to Ramipril 10 mg or Irbesartan 300 mg;
 - Has contraindications to RASB;
 - Does not have evidence or history of micro- or macroalbuminuria (as defined in 5.1.4) and is not being treated with RASB or other anti-hypertensive agents.

If the above criteria are met and Visits 2 and 3 are skipped, Visit 4 will be scheduled 3 weeks after Visit 1 with a window of 2 weeks before and 3 weeks after the target date. The collection of medical history and the physical exam scheduled at Visit 2 will be conducted at Visit 4.

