8. STUDY PROCEDURES

8.1. Schedule of Events

The schedule of events that will take place in the proposed study is outlined in Figure 1. Visits will be frequent during the Run-In period and during the first 30 days after randomization in order to escalate the allopurinol dosage and closely monitor the occurrence of AEs. After that, participants will be seen every 3-4 months to monitor their UA levels, renal function, occurrence of AEs, and medication compliance and, if necessary, to perform interventions to improve compliance. Visit 1 will be considered as Time 0 for scheduling Visits 2-5, Visit 5 will be considered as Time 0 for scheduling Visit 6-16, Visit 16 as Time 0 for scheduling Visit 17. The study windows that define when study visits may occur are noted in Figure 1 and differ by type of visit. Visits 2, 3, and 6 will be carried out within 6 business days (before or after) from their scheduled dates; visits 11, 16, and 17 within 2 weeks before and 4 weeks after their scheduled dates; visit 4A (if necessary) within 1 week before and 3 weeks after its scheduled date, and all other visits within 2 weeks (before or after) from their schedule dates. Additional blood or urine samples may be required in between visits if clinically significant changes are observed in blood or urine measurements that need to be confirmed or otherwise monitored. iGFR measurements may be repeated for medical reasons or technical problems (see 7.1). Safety laboratory tests (CBC, serum creatinine, K^+ , ALT, and pregnancy tests in women) will be performed by local laboratories. Outcome variables (plasma iohexol, serum creatinine and cystatin C, urinary AER), HbA1c, and serum uric acid will be measured by the Central Laboratory at the University of Minnesota, directed by [name].

Figure 1. Schedule of Events

Year	1	1	1	1	1	1	1	1	1	1	2	2	2	3	3	3	3	3
Week	-12	-9	-7	-3	0	4	16	32	48	64	80	96	112	128	142	156	164	
Visit #	1	2	3	4	4a*	5	6	7	8	9	10	11	12	13	14	15	16	17
^Type of Visit: In-Person Visit Required (V); Phone Call (C); Other Visit (In-Person or Remote Visit, O)	O	V	O	V	V	C	O	O	O	O	O	V	O	O	O	O	V	V
EVENT	Screen	Run-in				RANDO 100 mg	Allopurinol or placebo										Wash-out	
		200-400 mg										EOS						
Informed Consent	x	x																
Demographics	x																	
Initial Medical Hx		x																
Interval Medical Hx and BP Control			x	x	(x)		x	x	x	x	x	x	x	x	x	x	x	x
Concomitant Meds	x	x	x	x	(x)		x	x	x	x	x	x	x	x	x	x	x	x

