- f. Subjects taking drugs known to interact with allopurinol in causing bone marrow depression will be excluded from the study. White blood cell counts will be done before the study drugs are prescribed, and quarterly thereafter. The study drug should be temporarily discontinued should evidence of bone marrow depression ($WBC < 3500/mm^3$) be present and confirmed. WBC should be repeated two weeks after study drug discontinuation. If WBC recovers, consider re-challenging and repeating WBC two weeks after drug re-introduction. In addition, if WBC is confirmed to be $< 2500/mm^3$ and/or ANC is $< 1000/mm^3$, the event also needs to be reported as an AE. The Drug Monitoring Committee will review each case and decide whether a referral to a hematologist is warranted and whether study treatment can be reinstated after blood values have returned to normal. If drugs potentially causing bone marrow depression in combination with allopurinol are begun after entry into the trial, observations for this side effect will be intensified or, if recommended by the Drug Monitoring Committee, study drug may be interrupted.
- g. To minimize the risk of allergic reactions during the iGFR measurement, subjects with a history of iodine allergy will be excluded from the study.
- h. To minimize the risk of liver injury, subjects with clinically significant hepatic disease and/or elevated liver enzymes above 2.5 x the upper limit of normal at the screening visit will be excluded from the study. In those subjects that are enrolled in the study, liver enzyme levels will be monitored at each follow-up visit. If levels are abnormal, the measurement will be repeated and if values are confirmed to be elevated the study drug will be discontinued. The Drug Monitoring Committee will review each case and decide whether a referral to a hepatologist is warranted and whether study treatment can be reinstated after enzyme values have returned to normal on the recommendation of a hepatologist.
- i. To minimize the impact of blood draws, participants with low hemoglobin levels (< 11 g/dL in males, < 10 g/dl in females) will be excluded. Subjects will be advised not to donate blood while participating in the study and for two months after their participation has ended. If they have just donated blood, their screening for the study will be delayed by 3 months. Hemoglobin levels will be monitored quarterly.

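### After a confirmed potassium above 6.0 mEq, Section 8.3 restarts the RAS blocker at half dose after 72 hours with no off-drug potassium required first

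*Protocol*

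**What the plan says.** The rule is in Protocol Section 8.3 (Run-in Period). It is triggered by a potassium above 6.0 mEq or a serum creatinine more than 30% above baseline. The first step for the participant is: "immediately obtain a confirmatory lab value at their local lab or clinical site and then discontinue the RAS blocker while awaiting this confirmatory result". On confirmation, the instruction is: "If confirmed, the participant will resume RAS blockade at half dose 72 hours later and will have repeat labs one week later". Only if the abnormality is still present after that is RAS blockade stopped for the rest of the trial and blood pressure managed with other drugs. For potassium, the rule extends beyond run-in: "These same steps will be taken if hyperkalemia develops during the trial".

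Earlier in Section 8.3, a potassium above 5.5 mEq is given as an example of a contraindication, and participants with a contraindication are not to receive these drugs.

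Section 13.5 treats two other laboratory safety signals differently; both rules concern the study drug. After a confirmed low white cell count the drug is held and the count is repeated off drug two weeks later. The text then reads: "If WBC recovers, consider re-challenging and repeating WBC two weeks after drug re-introduction". After confirmed liver enzyme elevation, the Drug Monitoring Committee decides "whether study treatment can be reinstated after enzyme values have returned to normal on the recommendation of a hepatologist".

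**The concern.** The order of steps matters. The confirmatory sample comes first and the drug is stopped second, so a confirmed value above 6.0 describes the participant on the drug. It does not show what happens once the drug is withdrawn. The protocol then directs a restart after a fixed interval, and the first required repeat falls after the participant is back on treatment. No laboratory value, threshold or clinical decision is placed between confirmation and restart.

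The purpose of a hold is to learn whether the abnormality resolves. Here that information is not required until re-exposure is under way. If potassium has not come down within 72 hours, the participant receives more of a potassium-raising drug, and nothing in the required schedule would show this for several days. The same path applies to a confirmed creatinine rise.

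The trial itself starts these drugs or raises their dose, in people whose eGFR at entry may be as low as 40 ml/min/1.73 m², and lower with the age and diet adjustments (Section 5.1). Section 13.4.3 lists hyperkalemia and increased creatinine among the known risks of RAS blockers.

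**Working it through.** **1. Days of re-exposure before the next required potassium**

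The protocol states no such figure, so it has to be counted from the sentence in Section 8.3.

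- Day 0: confirmation of the abnormal value.
- Restart: 72 h ÷ 24 = day 3.
- Repeat labs, if the week runs from confirmation: day 7.
- Repeat labs, if the week runs from restart: day 3 + 7 = day 10.

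Re-exposure = day of repeat labs − day of restart.

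- Week from confirmation: 7 − 3 = **4 days**.
- Week from restart: 10 − 3 = **7 days**.

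The text does not say which count is meant, so the range is 4 to 7 days at half dose.

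**2. Could a routine visit fill the gap?**

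Figure 1 (Section 8.1) places the local potassium at weeks −12, −7 and −3 in the full run-in, then at weeks 4, 16, 32, 48, 64, 80, 96, 112, 128, 142, 156 and 164. Visit 5 at week 0 is a phone call with no local laboratory tests. Successive differences in weeks are:

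- Week −12 to week 4: 5, 4, 7
- Week 4 to week 128: 12, 16, 16, 16, 16, 16, 16, 16
- Week 128 to week 164: 14, 14, 8

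The gaps run from 4 to 16 weeks. A scheduled potassium would fall inside a given 72-hour hold only by chance. Participants newly started on a RAS blocker have one additional check, two weeks after reaching full dose. That check is not tied to a hold or a restart.

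**3. Does any other section require an off-drug value before restart?**

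| Protocol section | What it provides | Required before restart? |
|---|---|---|
| 8.1 | "Additional blood or urine samples may be required in between visits if clinically significant changes are observed in blood or urine measurements" | No: permissive, with no timing and no link to restart |
| 9.4 | Potassium at visits | No: follows the visit schedule |
| 13.4.3 | RAS-blocker adverse events will be monitored | No: general statement |
| 13.5, item j | Reduce the dose, then stop if the event continues | No: no check before restart |
| 14, item 4 | Detailed follow-up of abnormal results left to the Manual of Operations | Unknown: the Manual is not among the documents, and Section 8.3 does not cite it here |
| 14, item 6 | Drug Monitoring Committee discusses serious medication-related problems | No: no test and no timing |

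**4. Consistency with the protocol's own thresholds**

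A potassium above 5.5 mEq is a reason not to give a RAS blocker. The restart sentence applies to participants confirmed above 6.0 mEq and asks for nothing to show that the value has fallen below 5.5. The two instructions can conflict for the same participant, and the site has no required value to tell it which one applies.

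The potassium sentence is the same as in the December 2013 protocol. The off-drug white cell repeat and the recovery condition, by contrast, were added by a later amendment, so the sponsor has already made this type of change for another laboratory signal.

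**The case against.** The strongest counter-argument is the Manual of Operations. Section 14 makes it binding on clinics for any abnormal result, and it may already require a potassium before restart. The documents cannot exclude this, so whether sites actually lack the check is unsettled. It remains true that Section 8.3 gives a mandatory instruction without the check and does not refer the reader elsewhere. If the Manual has the step, the protocol sentence should carry it too.

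Second, sites do not act on one sentence alone. Site physicians, the participant's own physician and the Drug Monitoring Committee may all be involved, and a clinician who reads the 5.5 mEq contraindication beside the restart rule has good reason to recheck. That is likely in practice. But the contraindication is written for starting treatment, the restart sentence does not invoke it, and a safety instruction should not depend on sites doing more than it asks.

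Third, the comparison with white cells and liver enzymes is imperfect. Those rules govern the investigational drug, whereas RAS blockade is background standard of care, and withholding it has a cost in albuminuric patients. This is fair. It argues for a short hold and a clear restart threshold, but it does not justify restarting without a value.

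Fourth, the rule already contains confirmation, a 72-hour hold, a halved dose, mandatory repeat labs and permanent discontinuation if the abnormality continues. Nothing in the documents shows that participants have been harmed. These features reduce the risk and place a limit on how serious the point is. They do not supply the missing measurement.

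**Conclusion.** The concern holds and should be fixed. As written, Section 8.3 restarts a RAS blocker at half dose three days after a confirmed potassium above 6.0 mEq, or a confirmed creatinine rise above 30%, on elapsed time alone. The next required value comes after 4 to 7 days of re-exposure, depending on how the week is counted.

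This rests on the protocol text as it stands and on day 0 being the day of confirmation. The Manual of Operations has not been seen. The number of participants affected cannot be estimated, because the protocol gives no rate of potassium above 6.0. The point concerns participant safety under background therapy; it does not bear on the primary or secondary efficacy analyses.

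**What to change.** Amend the sentence in Section 8.3 as follows.

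- After a confirmed potassium above 6.0 mEq or a confirmed creatinine rise above 30%, measure local potassium and creatinine off drug before any restart, for example at 72 hours.
- Resume at half dose only if the value is below a restart threshold set by the sponsor's clinicians. For potassium, the protocol's own 5.5 mEq contraindication is a natural candidate.
- Otherwise keep holding the RAS blocker and manage blood pressure with other agents.
- State whether the one-week repeat labs are counted from confirmation or from restart.

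If the Manual of Operations already contains such a step, bring it into Section 8.3 or cite it there.

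The cost is one sentence in a protocol amendment, a memo to sites, one additional local blood draw per confirmed event, and a later return to RAS blockade for some participants.

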8.4. Enrollment in the Study and Randomization (Visit 5)

- At the end of the run-in period, eligibility will be re-assessed based on the BP measures obtained at Visits 4 or 4A (if applicable), HLA-based genetic susceptibility to allopurinol skin reactions^{36,37} (tested at Visit 4) and a valid baseline iGFR measurement. Participants who are eligible for randomization based on those measures (SBP ≤ 150 and DBP ≤ 95 mmHg) and a negative HLA B*58:01 test will be telephoned by the study coordinator to discuss how the

study medication should be taken and its potential side effects.

- Immediately after the phone call, the participants will be randomized.
- Immediately after randomization the first batch of study medication will be mailed to the participant by the research pharmacy along with written instructions on how to take it. Participants will be instructed to notify the study personnel by phone and start taking the study medication as soon as they receive it.
- If the participant is positive for HLA-based genetic susceptibility to allopurinol skin reactions, or acceptable BP measurements, or a valid iGFR measurement cannot be obtained, he/she will be discontinued from the study prior to randomization.

